3.2.4 Exclusion criteria for participating patients

- 1) Age less than 18 years;
- 2) Dead on arrival or die within 10 minutes of arriving at hospital;
- 3) Patients who have been transferred to the Cardiology Department from another department within the same hospital;
- 4) Patients who have registered in CPACS-2 study.

3.2.5 Data collection

Data to be collected at discharge:

From the beginning of the study, all clinical data will be collected for all discharged or deceased patients who was diagnosed as acute coronary syndrome in the emergency department and inpatient department. Data to be collected include demography, clinical manifestations, the medical treatments at the emergency room, during hospital stay, and at discharge, as well as adverse events during hospitalization, and prognosis (basic questionnaire, appendix 1), costs during hospitalization (appendix 2) and the patients' quality of life (appendix 3). At the same time, the mobile phone numbers of patients or their families are registered for

conducting the patient satisfaction survey through the SMS platform (patient satisfaction survey questionnaire, appendix 4).

Data to be collected at follow-ups:

Patients who are alive at discharge and sign the informed consent will be followed up twice (at 6 months and 12 months). Data collection at follow-ups includes lifestyle, medical treatments, rehabilitation, adverse events (myocardial infarction, stroke, revascularization, hospitalization and death) (follow-up questionnaire, appendix 5). A quality of life survey will be conducted at the second follow-up visit (QoL35, appendix 3).

Data collectors:

The information at discharge and follow-ups (appendix 2, appendix 3 and appendix 5) and the informed consent to patients should be completed by the medical doctor in the department who is trained and assigned the responsibility specifically.

Data entry staff:

[figure not shown]
The entry of data (appendix 1, appendix 2, appendix 3, appendix 5) shall be completed by an independent staff at medical fair management office who are not responsible for medical diagnosis and treatment.

Data collection process:

Data collectors complete the appendix 2 and 3 on the day or one day before the patient's discharge, check the address and valid phone numbers, get informed consent for follow-up, make the appointment for follow-up time, as well as inform the data entry staff to enter the patient's medical records and questionnaires into the CPACS-3 IT system. All the patients' data should be entered within 2 weeks.

When patient is discharged from hospital, the IT system will send satisfaction questionnaire automatically via SMS platform to the patients or their family members, and invite this patient to reply message. The replied message will be automatically entered into the database system.

At 6 months and 12 months after discharge, the patient will be followed up by either face-to-face or telephone.

The data collection process.

Storage of original data:

Hospitals participating in the study were required to set up registers and medical records at emergency department. The nurses at emergency department are required to record each patient's visit time (accurate to minutes) and narratives, and keep the records at least for 7 years after the end of the project. All patients admitted to the emergency room shall uniformly use the emergency medical records (including patient narratives, medical advices and laboratory test results).

Hospital inpatient department is required to record all patients' (both ACS and non-ACS) information in either electronic or paper records. These records should be saved 7 years after the end of the study, in case of project supervision.

Protection of privacy of patients' information:

Patients' ID information will be kept in the local hospitals together with other medical information and will comply with the local medical record confidentiality regulations. The electronic records are stored in the CPACS IT system, which cannot be accessed by anyone except the authorized personnel. Moreover, all the authorized personnel have strict levels of authority and cannot browse or modify other data beyond their authority. All electronic data will be protected by password. During data analysis, all patients' information will be de-identified, and it is

impossible to identify who is included in the study in the reports and published articles from the study.

3.2.6 Quality of care assessment

The quality of care assessment indicators include key performance indicators (KPIs) recommended by the ACC/AHA acute myocardial infarction quality of care assessment guidelines and patient satisfaction.

The KPIs and its definitions used to evaluate the overall effect of QCI are shown in table 1. After receiving the patient’s data, the CPACS-3 IT system will automatically produce the quality of care assessment report and update it in a real time. The web-based IT system can generate quality of care assessment report for any duration for each hospital. Hospital QCI team members can see the quality of care report of their own hospital in the system. Local health bureau and the provincial health department can view the reports of the hospitals within their respective authorities. The Ministry of Health and CPACS-3 study team can view all participating hospitals’ quality of care reports.

Table 1. KPIs and definitions

	KPI	Definition
1	Door to ECG time	The mean time from door to first ECG; and the Proportion of patients who had the first ECG traced within 10 minutes after hospital arrival.
2	Early use of Aspirin	Proportion of patients who received aspirin within 24 hours of arrival at hospital
3	Early use of Clopidogrel	Proportion of patients who received Clopidogrel within 24 hours of arrival at hospital
4	Early use of Statins	Proportion of patients who received statins within 24 hours of arrival at hospital
5	Aspirin prescribed at discharge	Proportion of patients who are prescribed aspirin at hospital discharge
6	Clopidogrel prescribed at	Proportion of patients with STEMI and NSTEMI who are prescribed Clopidogrel at hospital discharge

	discharge	
7	Beta-blocker prescribed at discharge	Proportion of patients who are prescribed a beta-blocker at hospital discharge
8	Statins prescribed at discharge	Proportion of patients who are prescribed a statin at hospital discharge
9	ACEI or ARB for Patients with LVSD	Proportion of patients with left ventricular systolic dysfunction (LVSD) who are prescribed angiotensin-converting–enzyme inhibitors(ACEI) or angiotensin-receptor blockers(ARB) at hospital discharge (for purposes of this measure, LVSD is defined as chart documentation of an left ventricular ejection fraction less than 40% or a narrative description of left ventricular systolic function consistent with moderate or severe systolic dysfunction)
10	Reperfusion therapy for STEMI patients	Proportion of STEMI patients who arrive hospital within 12 hours of symptom onset receiving fibrinolysis
11	Door to needle time	Proportion of AMI patients with ST-segment elevation or LBBB on the ECG closest to hospital arrival time receiving fibrinolytic therapy within 30 min from arrival to the hospital.
12	Length of stay	Mean days of hospitalization
13	Diagnosis inconsistent with examination findings	Proportion of patients with a final diagnosis inconsistent with biomarker findings

Patient satisfaction survey will focus on the experiences that the patient just went through in seeking the medical care, in order to determine the patient satisfaction level. We will ask about the reasons for patients’ dissatisfaction and the possible factors related to patient satisfaction including hygiene level of the ward, quietness

at night, communication satisfaction with nurses and doctors, timely responsive in case of problems, accessibility to the necessary information at discharge, overall satisfaction score and whether willing to recommend this hospital to others. The questionnaire will first be validated in a small group of people and to be used after proving its validity.

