CLINICAL PATHWAYS FOR ACUTE CORONARY SYNDROMES IN CHINA

**Phase 3
Quality Care Initiation
and Evaluation
Protocol**

Chinese Society of Cardiology

THE GEORGE INSTITUTE
for International Health

Table of Contents

1. Overview	3
2. Background	4
2.1 Burden of acute coronary disease in China.....	4
2.2 The CPACS-1 study.....	4
2.3 CPACS-2.....	5
3. CPACS phase 3 Study Plan	8
3.1 Aim	8
3.2 Methods.....	8
3.3 Quality control	18
4. Statistical analysis plan	19
4.1 Effectiveness evaluation	19
4.2 Basic situation evaluation	19
4.3 QCI evaluation	20
5. Process evaluation	20
6. Economic evaluation	20
7. Time schedule	20
8. Ethics	21
9. Governance and Organization	21
Reference	23

1. Overview

Clinical Pathway for Acute Coronary Syndromes in China (CPACS) are a series of trials initiated and conducted by Chinese Society of Cardiology and The George Institute for Global Health, supported by the Ministry of Health of China, aiming at shortening the gaps between clinical practice and evidence-based medicine and improve the prognosis of patients with acute coronary syndrome (ACS) through optimizing clinical processes in diagnosis, treatment and hospitalization of ACS patients. These trials were expected to provide evidence on the improvement of hospital services' quality by the interventions with the implementation of clinical pathways for ACS as the core, as well as cost-effectiveness analysis and analysis of the barriers in implementation.

CPACS-1 was a prospective registry and follow-up study, involving 51 tertiary or secondary hospitals in 18 provinces across the country. A total of 2973 ACS patients were included. The study found that there was a big gap between Chinese hospitals and guidelines in the treatment of ACS, for example, the final diagnosis and objective examination indicators were not consistent among 20% of patients. Less than half of the ACS patients were prescribed with the four drugs recommended in the guidelines (aspirin, beta receptor blocker, angiotensin-converting enzyme inhibitor and statin drugs) when they left the hospital (Heart 2008;94:554-560; Am Heart J 2009;157: 509-516).

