3.1 Aim

To improve the diagnosis and treatment of patients with ACS, explore the mode of care suitable to local health resources, and maximize the application of evidence-based medicine in China's remote county-level hospitals.

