- Education and training for QCI teams:** The participating hospital must receive the training provided by the project team when the QCI intervention starts, which includes introduction of intervention project, feedback pathway, introduction of online training, improvement and evaluation of medical quality, patient safety, and the conception of patient-centered services. Three key members of the hospital's QCI team are required to attend.
- Web-based education for relevant staff:** Problem-based learning modules linked to professional Chinese Continuing Medical Education (CME)

programs, will be provided to clinical staff working at different levels (principally doctors and nurses) in each hospital. The education includes ACS diagnosis and treatment knowledge, and also patient safety and health care quality. Staff will be required to register to participate and complete the modules on-line. The website will record log-in details for all registered staff and a compulsory knowledge test on the website will be provided before the training started. The test also could be done at any time when after learning module started. CME points will be redeemed on passing the test (a score over 90 in 100 points totally).

- **Online access to specialist advice using the “e-consultant” program:** The e-consultant program allows hospital clinicians to access expert advice from clinical cardiologists via a web-based system. The program will have two kinds of expert advices, the first one is a web-answering system, in which doctors in the intervention group could ask questions that they face during the ACS patients’ treatment and the expert will answer them in 24 hours; the second one is the case conference system, by which the hospital under intervention will received twice case discussion with cardiovascular experts on line.
- **Patient education:** Patient-oriented educational material will be provided to all ACS patients (and their families) during their admission to hospital. The material will focus on the importance of long-term medication use and lifestyle modification.

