3.2.9 Outcomes

The primary outcome will be the incidence rate of in-hospital major adverse cardiovascular events (MACE) comprising all-cause mortality, myocardial infarction or re-infarction and stroke. Secondary outcomes will be the key performance indicators (KPIs) and the patient satisfaction.

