4.2 Basic situation evaluation

GLMM model will also be used to compare the socio-anthropometric variables between the intervention groups, and between time periods, as well as between patients with different discharge diagnosis (STEMI, NSTEMI, UAP). If there is neither the time effect nor the interaction with the intervention, *t* test will be used to compare the difference of continuous variables between the intervention groups.

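### KPI 6 counts discharge clopidogrel only in patients diagnosed STEMI or NSTEMI, and the intervention targets diagnosis, so relabelling alone can move this one secondary outcome, by an unknown amount and in an unknown direction

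*Protocol*

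**What the plan says.** Table 1 in section 3.2.6 gives KPI 6 as "Proportion of patients with STEMI and NSTEMI who are prescribed Clopidogrel at hospital discharge". For the same drug on arrival, KPI 3 is "Proportion of patients who received Clopidogrel within 24 hours of arrival at hospital", with no restriction by subtype. KPIs 5, 7 and 8 are likewise unrestricted.

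Table 1 attaches no biomarker or ECG criterion to the STEMI/NSTEMI restriction in KPI 6. It does spell out LVSD for KPI 9, and it ties KPI 11 to the ECG nearest arrival. The one place where the protocol names the source of the subtype is section 4.2, which uses the discharge diagnosis (STEMI, NSTEMI or unstable angina).

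Diagnosis is one of the things the trial sets out to change:
- The aim in section 3.1 begins "To improve the diagnosis and treatment of patients with ACS".
- On the staff modules, section 3.2.7 says "The education includes ACS diagnosis and treatment knowledge".
- KPI 13 is "Proportion of patients with a final diagnosis inconsistent with biomarker findings". It is among the indicators reported to each hospital every six months, and the hospital's team must respond with solutions.
- The Overview reports that in CPACS-1 "the final diagnosis and objective examination indicators were not consistent among 20% of patients".

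Section 3.2.9 states "Secondary outcomes will be the key performance indicators (KPIs) and the patient satisfaction", so KPIs 6 and 13 are both secondary outcomes. Section 4.3 tests each for a treatment effect and a time effect with a GLMM.

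**The concern.** A proportion compared between control and intervention periods should have a denominator that the intervention cannot alter. KPI 6 lacks that protection. Its denominator depends on a diagnosis made after the hospital's phase is set, and two parts of the intervention, KPI 13 feedback and diagnosis teaching, act on that diagnosis.

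One way to resolve a mismatch between diagnosis and biomarkers is to move a patient across the line between unstable angina and NSTEMI, and that line is the KPI 6 boundary. If the intervention succeeds on KPI 13 in this way, KPI 6 compares differently composed groups before and after crossover. Randomising hospitals does not prevent this. The hospital and period terms of the GLMM do not absorb it either, because the change starts with the intervention and so falls on the treatment term.

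At stake is the interpretation of one secondary outcome: an apparent gain or loss in prescribing might be only a change in who is counted. Prescribing that changes because a diagnosis was corrected is a real effect; only the change in composition is an artefact.

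**Working it through.** The protocol gives no rate, power or sample size for KPI 6, so there is no stated figure to reproduce. The check has three parts.

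**1. Shift from relabelling alone**

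Assumed, not in the protocol: of 100 ACS patients, 50 are labelled MI; 60% of these (30) have clopidogrel at discharge; patients who change label have it in 40%; each patient's prescription is held fixed. With r patients moving:
- unstable angina to NSTEMI: KPI 6 = (30 + 0.4r)/(50 + r)
- NSTEMI to unstable angina: KPI 6 = (30 − 0.4r)/(50 − r)

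**2. Precision**

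From sections 3.2.8 and 3.2.10: 96 hospitals, four wedges of 24, five periods, 50 patients per hospital-period, ICC 0.10. The ICC is given in the sample size section for MACE and is borrowed here. Half of 50 gives m = 25 MI patients per hospital-period. I use the linear mixed model variance for a stepped wedge as an approximation on the risk-difference scale, with p = 0.6:
- σ² = 0.24 × 0.9/25 = 0.00864; τ² = 0.10 × 0.24 = 0.024
- U = 24(4+3+2+1) = 240; W = 24² + 48² + 72² + 96² = 17,280; V = 24(16+9+4+1) = 720
- numerator: 96 × 0.00864 × (0.00864 + 5 × 0.024) = 0.1067
- denominator: (96×240 − 17,280) × 0.00864 + (240² + 96×5×240 − 5×17,280 − 96×720) × 0.024 = 49.77 + 414.72 = 464.49
- SE = √(0.1067/464.49) = 0.0152, or 1.52 points

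The SE is 1.45 to 1.53 for ICC 0.05 to 0.20. With τ² = 0.24 × ICC/(1 − ICC) and σ² = 0.24/m it is 1.60. If correlation within a hospital decays between periods (cluster autocorrelation 0.8, also an assumption), it is 1.86.

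Chance of p < 0.05 with no prescription changed = Φ(d/SE − 1.96) + Φ(−d/SE − 1.96), where d is the shift:

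| Moved per 100 | Direction | KPI 6 | Shift (points) | SE 1.52 | SE 1.86 |
|---|---|---|---|---|---|
| 2.5 | into MI | 31/52.5 = 59.0% | −1.0 | 10% | 8% |
| 2.5 | out of MI | 29/47.5 = 61.1% | +1.1 | 11% | 9% |
| 5 | into MI | 32/55 = 58.2% | −1.8 | 22% | 16% |
| 5 | out of MI | 28/45 = 62.2% | +2.2 | 31% | 22% |
| 10 | into MI | 34/60 = 56.7% | −3.3 | 59% | 43% |
| 10 | out of MI | 26/40 = 65.0% | +5.0 | 91% | 77% |

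With a 10-point prescribing gap (60% against 50%) and SE 1.52, the chances are about 6% at 2.5 per 100, 9% to 11% at 5, and 20% to 38% at 10. With no gap the shift is zero.

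**3. The same patients over all ACS**

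Suppose the 50 unstable angina patients also have clopidogrel in 40% (20 of 50). Before relabelling, the all-ACS rate is (30 + 20)/100 = 50%. After 10 move into NSTEMI, it is (34 + 16)/100 = 50%. Moves between subtypes cancel exactly.

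**The case against.** The strongest case against has five parts.

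*The size is assumed.* The MI share, the prescribing rates and the net flow are not in the protocol, and neither is the direction. A step that is complete at crossover is generous when feedback comes every six months. This stands. A reader might take the 91% cell as the expected false-positive rate, or infer that KPI 6 will be inflated. The documents support neither: that cell is the least favourable corner of an illustration, and the shift can be in either direction or nil.

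*The 20% mismatch proves little.* It has no subtype and no direction, and it comes from a registry in which two-thirds of hospitals were tertiary. This also stands. It shows that there is room for relabelling, not how much to expect.

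*The pathways do not drive it.* A reader might infer that the separate STEMI pathway adds to the problem. It does not: STEMI and NSTEMI are both inside KPI 6, and NSTEMI shares its pathway with unstable angina. Only KPI 13 feedback and diagnosis teaching remain as the mechanism.

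*Table 1 does not say discharge diagnosis.* MI status could be set from recorded biomarkers, and such detail may belong in a SAP. The reading is an inference from section 4.2 and from the absence of another criterion in Table 1. But the restriction itself is fixed in the protocol, and nothing there ties it to objective findings.

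*An MI-only indicator is a legitimate choice.* Section 3.2.6 presents the KPIs as drawn from guideline measures for acute myocardial infarction. An all-ACS rate is a different quantity that still depends on a final ACS diagnosis made after crossover. This is fair, and it is why the all-ACS analysis should be added and not substituted. KPI 13 will show whether diagnostic consistency changed, but not which way patients moved, so it does not settle how to read KPI 6.

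**Conclusion.** The concern holds in limited form. KPI 6 can show a difference at crossover through movement between unstable angina and NSTEMI alone, and the planned GLMM cannot separate that from a change in prescribing. Under the stated assumptions (half labelled MI, a 20-point prescribing gap, 5 to 10 per 100 moved one way from crossover), the shift is 1.8 to 5.0 points against an SE of about 1.5 to 1.9 points. At 2.5 per 100, or at 5 per 100 with a 10-point gap, the chance of a false positive is about 6% to 11%. True direction and size are unknown.

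The point touches one secondary outcome. The primary outcome is counted over all ACS patients, so movement between subtypes does not change its denominator. KPI 10 (STEMI only) depends on a diagnosis label in a similar way, but it was not quantified here.

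**What to change.** Keep the STEMI/NSTEMI definition of KPI 6 in Table 1 for hospital feedback and as the named indicator. For the outcome analysis, add to section 4.3:

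1. Fit the same GLMM to clopidogrel at discharge over all ACS patients, the denominator already used for KPIs 3, 5, 7 and 8.
2. Tabulate the shares of STEMI, NSTEMI and unstable angina by intervention phase.
3. Attribute a KPI 6 effect to prescribing only if the all-ACS analysis agrees.

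Agreement should mean the same direction and a compatible size, not significance in both, because the all-ACS rate is diluted. If half are MI, a real 5-point change confined to MI patients becomes 2.5 points over all ACS. The SE there is about 1.1 points (formula above with m = 50 and p = 0.5: √(0.05594/457.92) = 0.0111). That is about 2.3 SE, against 3.3 SE for KPI 6 (5.0/1.52).

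The cost is one extra analysis and one tabulation from data already collected. The all-ACS version remains a different quantity and still depends on the final ACS diagnosis, so it removes only the artefact from moves between subtypes. The change concerns the denominator of a measure, not who should be treated.

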3.2.7 Intervention

Each hospital will implement a quality of care improvement (QCI) initiative comprising 6 components:

- **Establishment of a quality improvement team:** The Department of Medical Administration, the Ministry of Health of China will invite each hospital to establish an ACS quality improvement team with the Director of the hospital as the designated Team Leader. The team members will include directors of departments relevant to the treatment of ACS (i.e. Emergency and General Medical) and each team will take overall responsibility for the implementation of the quality improvement initiative at their hospital.
- **Establishment of a web-based IT system for quality management (Hospital performance audit and feedback):** Standard reports on the performance of each hospital in the quality of care provided to ACS patients will be generated at 6-monthly intervals by the web-based IT system and sent to the Hospital Director, local Health Bureaus and the Ministry of Health (Figure 4). The report will provide a summary report of the pre-specified key performance indicators (KPIs) (Table 1) at each hospital based on the results for all ACS patients admitted at the end of each 6 month cycle. The report will also provide a study benchmark, against which participating hospitals can assess their own performance. After receiving the feedback reports, the QCI group should meet to discuss about the solutions to the possible problems that are identified in the reports. The group should return the suggested solutions to the CPACS-3 study team and implement those solutions immediately.

[figure not shown]

Figure 4. Web-based IT system of CPACS-3 study.

- Implementation of a clinical pathway:** Clinical pathways for the management of STEMI and NSTEMI/unstable angina will be provided to each hospital and incorporated for use as part of the patient medical record. Hospitals will be encouraged to adapt the pathway to suit the local resources (including staff) and facilities. All participating hospitals should have a meeting every 6 months to summarize the KPIs of that time period, make corresponding adjustments to the clinical pathway and feedback them to the project team.
- Education and training for QCI teams:** The participating hospital must receive the training provided by the project team when the QCI intervention starts, which includes introduction of intervention project, feedback pathway, introduction of online training, improvement and evaluation of medical quality, patient safety, and the conception of patient-centered services. Three key members of the hospital's QCI team are required to attend.
- Web-based education for relevant staff:** Problem-based learning modules linked to professional Chinese Continuing Medical Education (CME)

programs, will be provided to clinical staff working at different levels (principally doctors and nurses) in each hospital. The education includes ACS diagnosis and treatment knowledge, and also patient safety and health care quality. Staff will be required to register to participate and complete the modules on-line. The website will record log-in details for all registered staff and a compulsory knowledge test on the website will be provided before the training started. The test also could be done at any time when after learning module started. CME points will be redeemed on passing the test (a score over 90 in 100 points totally).

- **Online access to specialist advice using the “e-consultant” program:** The e-consultant program allows hospital clinicians to access expert advice from clinical cardiologists via a web-based system. The program will have two kinds of expert advices, the first one is a web-answering system, in which doctors in the intervention group could ask questions that they face during the ACS patients’ treatment and the expert will answer them in 24 hours; the second one is the case conference system, by which the hospital under intervention will received twice case discussion with cardiovascular experts on line.
- **Patient education:** Patient-oriented educational material will be provided to all ACS patients (and their families) during their admission to hospital. The material will focus on the importance of long-term medication use and lifestyle modification.

